Note: Unless otherwise specified, all assessments, examinations, and sample collections should be performed on the same day before drug administration.

Screening Period: Routine examinations or examination results obtained at a tertiary hospital (or this hospital) within 28 days prior to the first dose (unless otherwise specified) and before signing the informed consent form (ICF) can be used for screening, and do not need to be repeated.

Treatment Period (DLT Evaluation Period): For the first intratumoral injection of CNSI-Fe, safety assessments will be performed on Day 7 (± 1 day), Day 14 (± 1 day), and Day 21 (± 1 day) after the first dose to evaluate DLT.

Maintenance Treatment Period: After the DLT evaluation is completed, subjects without unacceptable toxicity will continue to the maintenance treatment period if the investigator determines that the benefit of continued treatment outweighs the risk. During the maintenance treatment period, subjects will receive one more dose of the investigational drug (intratumoral injection to the lesion, tentatively scheduled for Day 1, the dosing regimen may be adjusted based on the PK characteristics of this study by the sponsor and investigator).

Early Termination/End of Treatment (EOT) Visit: This will be scheduled within 7 days after the decision to discontinue treatment. If the assessments required for the

EOT visit were performed within 7 days prior to the EOT visit, they do not need to be repeated.

Safety Follow-up: Subjects who have received at least one dose of the study drug will undergo a safety visit 28 days (± 3 days) after the last dose. If the assessments required for the safety visit were performed within 3 days prior to the safety visit, they do not need to be repeated.

Medical History and Treatment History: Collected during the screening period, including past medical history, medication history (concomitant treatments within 4 weeks prior to screening and currently ongoing), history of all previous tumors (including tumor stage, diagnosis date, genetic test results), history of all previous anti-tumor treatments, family history, surgical history, immunization history, allergy history, smoking history, alcohol history, history of drug abuse/dependence, etc.

Vital Signs: Including respiratory rate, pulse/heart rate, blood pressure, and body temperature. Measured during screening, within 2 hours before CNSI-Fe administration, 1.5 hours (± 30 minutes) after administration, on Days 7, 14, and 21 of each cycle, at the End of Treatment (EOT) visit, and during the safety follow-up visit (excluding telephone visits).

Physical Examination: Including general condition, skin and mucosa, lymph nodes,

head, neck, chest, abdomen, spine, limbs, and nervous system. A complete physical examination will be performed during screening, before CNSI-Fe administration, at the EOT visit, and during the safety follow-up visit (excluding telephone visits). Symptom-directed physical examinations will be performed during the treatment period as clinically indicated.

Body Weight: Measured during screening and before CNSI-Fe administration.

ECOG performance status, complete blood count, urinalysis, blood chemistry, coagulation function, pregnancy test (for women of childbearing potential), and tumor marker tests should be completed within 7 days prior to the first dose of the investigational drug.

12-lead ECG: Performed during screening, within 2 hours before CNSI-Fe administration, 0.5 hours (± 5 minutes), 4 hours (± 30 minutes), 8 hours (± 30 minutes), 24 hours (± 30 minutes), 48 hours (± 30 minutes), and 72 hours (± 30 minutes) after administration, on Days 7, 14, and 21 of each cycle, at the EOT visit, and during the safety follow-up visit (excluding telephone visits). Continuous cardiac monitoring will also be performed for 8 hours after CNSI-Fe administration. Additional 12-lead ECG assessments may be added during the study to ensure subject safety, at the discretion of the investigator.

Echocardiography: Left ventricular ejection fraction (LVEF). Performed during screening, and as needed during the study period if there are clinically significant ECG abnormalities.

Concomitant Medications: All concomitant medications and treatments from the time of ICF signing until 28 days after the last dose or the start of a new anti-cancer therapy (whichever occurs first) should be recorded in the patient's medical records and reported in the electronic case report form (eCRF), including the name, reason for use, dose, route of administration, frequency, start date, and stop date.

Adverse Events (AEs): Only serious adverse events (SAEs) related to the protocol-specified procedures should be reported before the start of study drug treatment. After the start of study treatment, all AEs should be reported, regardless of their relationship to the study drug, until 28 days after the last dose. The investigator should follow up on all AEs until the event resolves to baseline or better, is considered stable by the investigator, the subject is lost to follow-up, or the subject withdraws consent. For all SAEs related to the investigational product or study procedures, every effort should be made to follow up until a final outcome can be reported.

Blood routine: Red blood cell count (RBC), hemoglobin (Hb), hematocrit, white blood cell count (WBC) and differential count (neutrophils, eosinophils, lymphocytes, monocytes, basophils and others) and platelet count (PLT). To be performed within 7

days prior to first dose of study drug in the screening period, on Day 7, Day 14, Day 21 of each cycle, at the End of Treatment (EOT) visit, and at the safety follow-up visit (excluding telephone visits). Additional blood routine tests can be performed as needed based on the investigator's clinical judgment.

Urinalysis: Urine specific gravity, urine pH, urine glucose, urine protein, urine ketone, urine red blood cells and urine white blood cells. To be performed within 7 days prior to first dose of study drug in the screening period, on Day 7, Day 14, Day 21 of each cycle, at the EOT visit, and at the safety follow-up visit (excluding telephone visits).

Biochemistry: Glucose, blood urea nitrogen (BUN) or urea, creatinine (Cr), sodium, potassium, magnesium, chloride, calcium, phosphorus, total bilirubin (TBIL), alanine aminotransferase (ALT), aspartate aminotransferase (AST), alkaline phosphatase (ALP), lactate dehydrogenase (LDH), total protein, albumin, triglycerides, total cholesterol, amylase, lipase. To be performed within 7 days prior to first dose of study drug in the screening period, on Day 7, Day 14, Day 21 of each cycle, at the EOT visit, and at the safety follow-up visit (excluding telephone visits). Additional biochemistry tests can be performed as needed based on the investigator's clinical judgment.

Coagulation function: International normalized ratio (INR), prothrombin time (PT), activated partial thromboplastin time (aPTT), thrombin time (TT), fibrinogen (FIB). To be performed within 7 days prior to first dose of study drug in the screening period,

on Day 7, Day 21 of each cycle, at the EOT visit, and at the safety follow-up visit (excluding telephone visits).

Pregnancy test: For female subjects of childbearing potential only; to be performed within 7 days prior to first dose of study drug in the screening period, at the EOT visit, and at the safety follow-up visit (excluding telephone visits). Pregnancy tests other than screening can be either serum or urine pregnancy tests, as per the investigator's judgment. If a urine pregnancy test is positive, it must be confirmed by a serum pregnancy test.

FSH test: For post-menopausal female subjects over 45 years of age but less than 55 years of age (see Section 4.1), a serum FSH test will be performed during the screening period to confirm post-menopausal status. If the subject is confirmed to be post-menopausal, no further pregnancy testing will be required; otherwise, she will undergo pregnancy testing like female subjects of childbearing potential.

Viral serology: Including hepatitis B virus (HBV) - [hepatitis B surface antigen (HBsAg), hepatitis B surface antibody (HBsAb), hepatitis B core antibody (HBcAb), hepatitis B e antigen (HBeAg), hepatitis B e antibody (HBeAb)], hepatitis C virus (HCV) - [HCV-Ab] and human immunodeficiency virus (HIV) - [Anti-HIV] testing.

HBV quantitative requirement: During screening, test the 5 HBV markers, if HBsAg is positive, HBV DNA testing is required; if HBsAg is negative but HBcAb is positive,

HBV DNA testing is also required. HCV quantitative requirement: During screening, test for HCV-Ab to determine if the subject has HCV infection, if HCV-Ab is positive, HCV RNA quantitative testing is required.

Iron tests: Serum iron (Fe), total iron binding capacity (TIBC), serum ferritin (SF), transferrin saturation (TSAT). To be performed during screening, within 24 h prior to CNSI-Fe dosing, at 5 min \pm 1 min, 15 min \pm 2 min, 30 min \pm 5 min, 2 h \pm 30 min, 6 h \pm 30 min and 10 h \pm 30 min post-dosing, on Day 7, Day 14, Day 21 of each cycle, at the EOT visit, and at the safety follow-up visit (excluding telephone visits). Additional iron tests may be performed as needed for subject safety during the study.

Tumor marker detection: carcinoembryonic antigen (CEA), alpha-fetoprotein (AFP), cancer antigen 125 (CA125), cancer antigen 15-3 (CA15-3), cancer antigen 19-9 (CA19-9), etc. Researchers will select appropriate tumor markers based on the situation. These will be tested within 7 days before the first dose of the study drug, on Day 21 of each cycle, at the End of Treatment (EOT) visit, and during the safety follow-up (excluding telephone visits).

Cardiac enzymes: lactate dehydrogenase (LDH), creatine kinase (CK), creatine kinase-MB (CK-MB), aspartate aminotransferase (AST), hydroxybutyrate dehydrogenase (HBDH). These will be tested during the screening period, and supplementary testing will be performed during the study period if the subject

experiences chest pain, palpitations, or ECG abnormalities.

PK blood sample collection: In Cycle 1: within 1 hour before CNSI-Fe dosing, and at 5 min \pm 1 min, 10 min \pm 2 min, 15 min \pm 2 min, 30 min \pm 5 min, 1 h \pm 10 min, 2 h \pm 10 min, 4 h \pm 15 min, 8 h \pm 15 min, 12 h \pm 30 min, 24 h \pm 30 min, 48 h \pm 1 h, and 72 h \pm 2 h after dosing. In Cycle 2 (if applicable), the sampling schedule may be adjusted based on the PK results from Cycle 1.

Collection of tumor tissue samples (PD/intratumoral PK sampling): For subjects who consent to provide archived or fresh tumor tissue samples from the target lesion, the samples will be obtained during the screening period. For PD samples, they should be collected within 24 hours to 17 days after the first dose (specific timepoint to be determined based on clinical practice), and at disease progression as clinically indicated. For intratumoral PK samples, they should be collected within 21 days after the first dose (specific timepoint to be determined based on clinical practice). Tumor tissue samples will only be transported for subjects who are eligible for enrollment.

Tumor assessment: Baseline imaging assessments will be performed within 28 days prior to the first study treatment (if the patient underwent imaging as part of routine clinical care prior to signing the ICF, and the imaging modality and location meet the protocol requirements, the results may be used for screening upon investigator approval). Baseline tumor evaluation should include the chest, abdomen, pelvis, head (to exclude brain metastases), and any other suspected tumor sites. Subsequent evaluations should re-assess all measurable and evaluable lesions identified at

baseline, including the chest, abdomen, pelvis, and any other suspected tumor sites. The imaging modality used for tumor assessment during the study must be consistent with the baseline assessment. Subjects will undergo tumor assessment every 3-4 weeks during the treatment period, and every 7-8 weeks during the maintenance period (the investigator may decide to perform additional imaging assessments based on changes in the subject's condition; the first tumor assessment must be performed at weeks 3-4). Subjects with a confirmed complete response (CR) or partial response (PR) at the first assessment will require confirmation at least 4 weeks later. Tumor imaging may be omitted at the early termination/withdrawal visit if it was performed within th

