The basis for dose selection: According to the "Guidance Principles for Estimating the Maximum Recommended Starting Dose for First-in-Human Clinical Trials of Healthy Adult Volunteers" issued by the NMPA, and with reference to the Maximum Recommended Starting Dose (MRSD) for anticancer drugs in ICH S9 "Nonclinical Evaluation for Anticancer Pharmaceuticals", the design of the dosage regimen depends on the data from the long-term toxicity studies of CNSI-Fe in animals. In the toxicity study with 2 intramuscular injections on Day 1 and Day 4, followed by a 4-week recovery period in rats, the Highest Non-Severely Toxic Dose (HNSTD) was 20 mg/kg (calculated as Fe²⁺), corresponding to a Human Equivalent Dose (HED) of 3.6 mg/kg; in the toxicity study with Beagle dogs, the HNSTD was 15 mg/kg, corresponding to an HED of 8.7 mg/kg. Assuming an adult body weight of 60 kg and a safety factor of 6, the MRSD for humans is estimated to be approximately 0.6

mg/kg and 1.45 mg/kg, respectively.

Considering the effective doses in preclinical studies, in multiple solid tumor xenograft models (human colon cancer COLO 205, human breast cancer MDA-MB-231, human breast cancer HCC1954, and human colon cancer HT-29 cells), CNSI-Fe (calculated as Fe²⁺, 0.1875 mg, 0.375 mg, 0.50 mg, 0.75 mg, administered twice on Day 1 and Day 4) significantly inhibited tumor growth. The effective dose and the maximum effective dose were 0.1875 mg and 0.75 mg, respectively. Assuming a mouse body weight of 20 g and an adult human body weight of 60 kg, the corresponding human equivalent doses are 0.84 mg/kg and 3.36 mg/kg, respectively.

Considering the above factors and the safety of the first-in-human trial, this study selected 0.5 mg/kg as the starting dose, with escalating doses of 0.5 mg/kg, 1.0 mg/kg, and 1.5 mg/kg. Calculated based on an average human body weight of 60 kg, the escalating doses are 30 mg, 60 mg, and 90 mg (calculated as Fe²⁺). If ≥2 subjects experience DLT at the 90 mg dose, the dose will be reduced to 75 mg for safety and tolerability observation; if the dose escalation to 90 mg does not reach the MTD, the SRC will discuss whether to further escalate the dose to 120 mg, 150 mg, or even higher, based on the available safety, PK/PD, and preliminary efficacy data (if 120 mg still does not reach the MTD, the SRC will discuss whether to stop the dose escalation or directly proceed to 150 mg or even higher doses).

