This study will enroll patients with advanced solid tumors and use the traditional "3+3 method" for dose escalation. The dose escalation principle is: in any dose cohort, 3 subjects will be enrolled first. If none of the first 3 subjects experience DLT during the DLT evaluation period, the next dose cohort can be entered. If ≥ 2 of the first 3 subjects experience DLT during the DLT evaluation period, dose escalation will be stopped (for the 30 mg cohort, if 2 DLTs occur, the sponsor and investigator will jointly decide whether to reduce the dose and continue exploration). If 1 of the first 3 subjects experiences DLT during the DLT evaluation period, an additional 3 subjects will be enrolled in that dose cohort, and if ≤ 1 of the 6 subjects in that dose cohort experience DLT during the DLT evaluation period, the next dose cohort can be entered; if ≥ 2 of the 6 subjects in that dose cohort experience DLT during the DLT

evaluation period, dose escalation will be stopped. The dose prior to the dose at which $\geq 2/3$ or $\geq 2/6$ subjects experience DLT during the DLT evaluation period will be determined as the MTD (if only 3 subjects are enrolled in a cohort, an additional 3 subjects will need to be enrolled).

The “3+3” dose escalation principle

The number of subjects who experienced a dose-limiting toxicity (DLT) within a particular dose cohort	dose escalation principle
0/3	no DLT is observed in the 3 newly enrolled subjects
0/3	no DLT is observed in the 3 newly enrolled subjects
$\geq 2/3$	Dose escalation should be stopped, and that dose will be considered the Maximum Administered Dose (MAD). If the previous lower dose was only administered to 3 subjects, then 3 more subjects need to be enrolled
1/3	
If the 3 newly enrolled subjects in the dose group do not experience a DLT (Dose-Limiting Toxicity), then the study will proceed to the next dose group.
 
 ● ● If ≥ 1 of the 3 newly enrolled subjects in the dose group experience a DLT, then dose escalation will be stopped, and that dose level will be considered the MAD (Maximum Administered Dose). The previous dose level will be considered the MTD (Maximum Tolerated Dose) (if the dose group only had 3 subjects, then an additional 3 subjects will need to be enrolled).

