The DLT (Dose-Limiting Toxicity) evaluation period is in the first cycle, i.e., within 21 days after the first dose. This stage is tentatively set with 3 dose groups (calculated as Fe^{2+} , 30 mg, 60 mg, 90 mg). If ≥ 2 subjects in the 90 mg group observe DLT, the dose will be reduced to 75 mg for safety and tolerability observation; if the dose is increased to 90 mg and MTD (Maximum Tolerated Dose) is still not reached, the SRC

(Safety Review Committee) will discuss continuing to escalate the dose to 120 mg, 150 mg, or even higher (if MTD is still not reached at 120 mg, the SRC will discuss whether to stop dose escalation or directly proceed to 150 mg or even higher doses).

After 3-6 subjects in each dose group have completed the DLT evaluation, the SRC will evaluate the overall safety of each dose group based on the data obtained and determine whether to continue escalating to the next dose group or to determine the recommended dose for subsequent clinical development.

Enrollment Interval: To fully protect the safety of the subjects, during the dose escalation process, the first subject in each dose group must be dosed at least 3 days after the first dose, and the remaining subjects in that dose group can then start the first dose. The interval for subsequent subjects in the same dose group can be controlled at the discretion of the investigator. The last subject in each dose group must complete the DLT evaluation, and the safety and tolerability must be reviewed by the SRC before the first subject in the next dose group can receive the first dose.

Subject Replacement: During the DLT evaluation period, if a subject is unable to be evaluated for DLT (e.g., the subject's dose of the study drug did not reach at least 80% of the protocol-specified dose, or the subject discontinued study treatment before completing the DLT evaluation period for reasons other than DLT), additional subjects will need to be enrolled to make up the corresponding number in that dose

group.

DLT Definition: This study will grade toxicities according to NCI CTCAE v5.0. DLT refers to the following toxicity reactions that are considered by the investigator and/or the sponsor to be definitely or possibly related to the study drug CNSI-Fe, occurring within the first cycle (i.e., within 21 days after the first dose):

Hematological toxicity:

- (1) Any grade 4 hematological toxicity;

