- (2) Any grade 3 hematological toxicity that persists for >7 days after best supportive care, or grade 3 thrombocytopenia with bleeding tendency or requiring platelet transfusion;
- (3) Grade 3 neutropenia with fever, defined as: ANC<1×10⁹/L and a single temperature >38.3°C or sustained temperature ≥38°C for >1 hour.

Non-hematological toxicity:

- (1) Grade 3 cardiac toxicity that persists for >3 days after best supportive care, or grade 4 cardiac toxicity;
- (2) Grade 3 hepatic toxicity (for subjects with liver or bone metastases, and baseline grade 2 liver transaminases, ALT, AST or ALP >10×ULN) that persists for >3 days after best supportive care, or grade 4 hepatic toxicity;
- (3) Any grade 3 non-hematological toxicity (excluding laboratory tests) that persists

for >7 days after best supportive care, except for grade 3 nausea, vomiting or diarrhea;

(4) Any grade 4 non-hematological toxicity (excluding laboratory tests);

(5) Any grade 3 or 4 non-hematological laboratory abnormality, if:

It requires medical intervention;

Or leads to hospitalization;

Or persists at grade 3 or above for ≥ 7 days after drug discontinuation.

Others:

(1) Any grade 5 toxicity;

(2) Other grade toxicities that the investigator and sponsor agree require early termination of CNSI-Fe treatment.

This study will not only observe the safety and tolerability of CNSI-Fe, but also preliminarily evaluate the efficacy of CNSI-Fe in patients with advanced solid tumors.

The investigators will evaluate the efficacy of CNSI-Fe based on the results of imaging examinations [computed tomography (CT), positron emission tomography (PET)/CT, or magnetic resonance imaging (MRI)], referring to the revised RECIST v1.1 and RECIST v1.1.

Contrast-enhanced CT or contrast-enhanced MRI is the preferred imaging method for evaluating tumor response. If the subject is known to be allergic to the contrast agent, if possible, obtain a contrast agent evaluation using local preventive standards, or use

alternative methods. In cases where contrast agents are strictly contraindicated, non-contrast scans should be performed. If the subject is contraindicated for contrast-enhanced CT scans, a non-contrast chest CT scan and contrast-enhanced abdominal and pelvic MRI scan can be performed.

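### On the text available, the 3-day pause after the first subject of each dose group can end 2 to 5 days before that subject's first scheduled post-dose blood count and biochemistry

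*Combined protocol and SAP*

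**What the plan says.** The synopsis paragraph on the basis for dose selection places the trial as first-in-human: "Considering the above factors and the safety of the first-in-human trial, this study selected 0.5 mg/kg as the starting dose".

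The Enrollment Interval paragraph gives the stagger within a group as "at least 3 days after the first dose, and the remaining subjects in that dose group can then start the first dose". It then leaves later spacing open: "The interval for subsequent subjects in the same dose group can be controlled at the discretion of the investigator". Neither sentence names data to be looked at, or a person to look at them, before the remaining subjects are dosed. The paragraph does state a review between groups: "the safety and tolerability must be reviewed by the SRC before the first subject in the next dose group can receive the first dose".

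The laboratory schedule is in the notes to Table 1-1. On the DLT evaluation period they say: "For the first intratumoral injection of CNSI-Fe, safety assessments will be performed on Day 7", with a window of 1 day either side, and again around Days 14 and 21. The Blood routine and Biochemistry notes give a screening sample within 7 days before dosing, then Days 7, 14 and 21 of each cycle. Extra tests are left to the investigator's judgment.

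**The concern.** The paragraph says that the interval is there to protect subjects. A pause does that only for toxicities that can be seen while it lasts. Two DLT criteria are defined by severity alone, with no duration or symptom condition, and can be silent. One is "Any grade 4 hematological toxicity". The other is the second part of the hepatic criterion, which ends "persists for >3 days after best supportive care, or grade 4 hepatic toxicity". Both need a laboratory result to be noticed if the subject feels well, and no blood count or liver panel is scheduled inside the pause.

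The stake is exposure. The other two of the first three subjects at a level could receive the same dose while a DLT in the first subject is present but unmeasured.

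**Working it through.** The plan states no figure on this point, so the check sets schedules side by side and counts days.

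**1. What is scheduled in the first 72 h** (synopsis and Table 1-1 notes)

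| Assessment | Post-dose times within the pause |
|---|---|
| Vital signs | 1.5 h |
| 12-lead ECG | 0.5, 4, 8, 24, 48, 72 h, plus 8 h continuous monitoring |
| Iron tests | 5, 15, 30 min; 2, 6, 10 h |
| PK samples (serum iron) | 5 min to 72 h, including 48 h ± 1 h |
| Adverse events | continuous |
| Cardiac enzymes, including AST | only if chest pain, palpitations or an ECG abnormality |
| Blood count | none; next on Day 7 |
| Biochemistry, including ALT, AST, bilirubin | none; next on Day 7 |

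**2. Gap from release to the first scheduled panels**

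Gap = max(0, elapsed days to the Day 7 visit − elapsed days to release). The earliest release is 3 elapsed days, which is study Day 4 if the injection is Day 1.

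- Injection counted as Day 1 (Study Design, Treatment Period): Day 7 is 6 elapsed days, or 5 to 7 with the window. Gap = 5 − 3 to 7 − 3 = 2 to 4 days.
- Day 7 counted after the dose (Table 1-1 notes): 7 elapsed days, or 6 to 8 with the window. Gap = 6 − 3 to 8 − 3 = 3 to 5 days.
- Both readings together: 2 to 5 days. The window is stated for the safety visits and is not repeated in the laboratory notes. Without it the gap is 6 − 3 = 3 or 7 − 3 = 4 days.

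Three days is a minimum. For later release, in elapsed days, the gap over both readings is:

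| Release | Gap (days) |
|---|---|
| 3 | 2 to 5 |
| 4 | 1 to 4 |
| 5 | 0 to 3 |
| 6 | 0 to 2 |
| 7 | 0 to 1 |
| 8 or later | 0 |

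**3. Subjects exposed**

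The 3+3 rule enrols 3 subjects first, so up to 3 − 1 = 2 more of the first three at a level could be dosed in the gap. None is affected if both are dosed after the first subject's Day 7 results.

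**4. Delay if the panels are drawn early**

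Assumptions, not in the documents: laboratory turnaround 4 to 24 h, review 2 to 24 h.

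- At the 48 h ± 1 h draw: earliest 47 + 4 + 2 = 53 h, latest 49 + 24 + 24 = 97 h. Delay past 72 h: 0 to 97 − 72 = 25 h.
- At the 72 h ± 2 h draw: earliest 70 + 4 + 2 = 76 h, latest 74 + 24 + 24 = 122 h. Delay: 4 to 50 h.

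The 48 h draw is the better place.

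**The case against.** The strongest objection is that only part of the protocol can be read. The Table 1-1 grid is not shown, the text breaks off in the tumor assessment note, and the synopsis points to later sections and a laboratory manual. The interval sentence is also garbled: taken literally, it has the first subject dosed 3 days after the first dose. A word for observation may have been meant. A reader might infer that nobody looks at the first subject's data before the others are dosed. The documents do not support that. Investigators would see the ECGs and adverse events in any case, and a release rule may stand in text that is not shown. The laboratory timing does not depend on this, because the Blood routine and Biochemistry notes are legible and give Day 7.

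The pause is also not arbitrary. It matches the ECG and PK schedule, and it covers acute cardiac and iron effects. Spacing can be longer and extra tests are allowed. That stands, and it limits the point to blood counts and biochemistry.

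The harm needs several conditions together: a grade 4 laboratory toxicity in the first subject, present within the pause, without symptoms, with no discretionary test, and the others dosed early. The documents available give no onset time. That stands too, and it is why the point claims no frequency.

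Two further inferences should be resisted:

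- That an early result would by itself stop the group. Under the Dose Escalation rule, "If 1 of the first 3 subjects experiences DLT during the DLT evaluation period, an additional 3 subjects will be enrolled", so a single DLT adds subjects. The suspension criteria list no single laboratory DLT, but they do include a judgment on the incidence and severity of adverse drug reactions, so suspension is possible and not automatic. An early test is therefore useful only with a stated hold rule.
- That 2 subjects at each of 3 planned levels, 2 × 3 = 6, caps the number affected. It does not, because the synopsis allows a 75 mg group, 120 mg, 150 mg or higher, and replacement subjects.

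**Conclusion.** The point holds as a design improvement worth considering, with medium confidence. Followed as written, the schedule lets the pause end 2 to 5 days before the first scheduled test that could show a silent grade 4 haematological or hepatic DLT in the first subject. Up to 2 more of the first three subjects at that level could be dosed in that time.

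This rests on three assumptions: that the garbled sentence means 3 elapsed days after the first subject's dose, that the others are dosed near that minimum, and that no earlier panel or release rule appears in text that is not shown. It does not show that the doses are unsafe, that safety oversight is absent or that any stated figure is wrong. The yield of one early draw is unknown.

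**What to change.** For the first subject of each dose level, add blood count and biochemistry to the existing 48 h PK draw. In the Enrollment Interval paragraph, reword the garbled sentence and state:

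1. The remaining subjects may be dosed only after the investigator and the sponsor have reviewed these results with the ECG and adverse event data, and have informed any other dosing site (3 to 6 centers are expected).
2. Dosing is held for an SRC decision only if an event meets a criterion in the DLT Definition, or could meet one if it persists. Liver enzymes are judged with the adjustment already given there for subjects with liver or bone metastases and grade 2 baseline values (>10×ULN).

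A hold for every new grade 3 laboratory value would be too broad. Subjects with liver metastases may enter with AST and ALT up to 5×ULN, so a modest rise could stop dosing for something that the plan does not count as a DLT.

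Keep the Day 7, 14 and 21 tests, since one early draw cannot settle the duration-based criteria or exclude later toxicity. Leave the 3+3 counting unchanged. If the full protocol already contains a release review, copy it into the synopsis and add only the 48 h panels and the hold criterion.

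The cost is a few sentences, one line in each of two laboratory notes, and one extra set of routine tubes for one subject per level, with no new visit. Release may be delayed by 0 to 25 h beyond 72 h under the assumptions above, and a hold would add the time that the SRC needs.
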